**Table 4 Case Definitions of Probable and Confirmed Myocarditis, Pericarditis, and Myopericarditis**

Condition	CDC Definition
Acute myocarditis	PROBABLE: Presence of $\geq 1$ new or worsening of the following clinical symptoms:  
 
Chest pain, pressure, or discomfort
 
Dyspnea, shortness of breath, or pain with breathing
 
Palpitations
 
Syncope
 
 AND $\geq 1$ new finding of 
 
Troponin level above upper limit of normal (any type of troponin)
 
Abnormal ECG or rhythm monitoring findings consistent with myocarditis
 
Abnormal cardiac function or wall motion abnormalities on echocardiogram
 
cMRI findings consistent with myocarditis
 
 AND 
 
No other identifiable cause of the symptoms and findings
 

	CONFIRMED: Presence of $\geq 1$ new or worsening of the following clinical symptoms:  
 
Chest pain, pressure, or discomfort
 
Dyspnea, shortness of breath, or pain with breathing
 
Palpitations
 
Syncope
 
 AND $\geq 1$ new finding of 
 
Histopathologic confirmation of myocarditis
 
cMRI findings consistent with myocarditis in the presence of troponin level above upper limit of normal (any type of troponin)
 
 AND 
 
No other identifiable cause of the symptoms and findings
 

Acute pericarditis	Presence of $\geq 2$ new or worsening of the following clinical features: 
 
Acute chest pain
 
Pericardial rub on exam
 
New ST-elevation or PR-depression on ECG
 
New or worsening pericardial effusion on echocardiogram or MRI
 

Myopericarditis	This term may be used for patients who meet criteria for both myocarditis and pericarditis.

Abbreviations: AV = atrioventricular; CDC = Centers for Disease Control and Prevention; cMRI = cardiac magnetic resonance imaging; ECG = electrocardiogram; ESC = European Society of Cardiology; MRI = magnetic resonance imaging.

- Persons who lack the listed symptoms but who meet other criteria may be classified as subclinical myocarditis (probable or confirmed).
- Using the Dallas criteria [Aretz 1987]. Autopsy cases may be classified as confirmed clinical myocarditis on the basis of meeting histopathologic criteria if no other identifiable cause.
- To meet the ECG or rhythm monitoring criterion, a probable case must include at least one of 1) ST-segment or T-wave abnormalities; 2) Paroxysmal or sustained atrial, supraventricular, or ventricular arrhythmias; or 3) AV nodal conduction delays or intraventricular conduction defects.
- Using either the original or the revised Lake Louise criteria [Ferreira 2018].
- Based on the 2015 ESC Guidelines for the diagnosis and management of pericardial diseases [Adler 2015].
- Typically described as pain made worse by lying down, deep inspiration, or cough, and relieved by sitting up or leaning forward, although other types of chest pain might occur.

Adapted from Gargano 2021.

**Table 5 Management of Suspected Myocarditis, Pericarditis, and Myopericarditis Cases**

Clinical Presentation	Procedures
Probable or Confirmed Myocarditis, Pericarditis or Myopericarditis	
 
1) ER visit and evaluation by a physician (as per national/local guidelines): 
 
a. Diagnostic work up might include: 
 
i. CBC, Inflammatory markers: ESR, CRP
 
ii. Cardiac markers: Troponin I, BNP, NT-proBNP
 
iii. Chest radiograph
 
iv. ECG
 
 
 
 
 
2) Evaluation by a cardiologist/pediatric cardiologist (as applicable) 
 
a. Follow AHA or other national/local guidelines 
 
i. Diagnostic work might include: 
 
1. Stress test echocardiogram
 
2. Cardiac biopsy
 
3. cMRI
 
4. Other laboratory or cardiac assessment tests as applicable
 
 
 
 
 
b. Follow up until resolution
 
 
 

Abbreviations: AHA = American Heart Association; BNP = brain natriuretic peptide; CBC = complete blood count; cMRI = cardiac magnetic resonance imaging; CRP = C-reactive protein; ECG = electrocardiogram; ER = emergency room; ESR = erythrocyte sedimentation rate; NT-proBNP = N-terminal pro b-type natriuretic peptide.

#### 8.2.3.2.2 Electrocardiograms

All participants will undergo a baseline ECG at Day 1 prior to study vaccine administration. Baseline ECGs will be read and interpreted by a Central Cardiac Adjudication Committee only as a comparison with new ECG(s) in the event that the participant experiences a cardiac event during the 28 days following vaccine administration that requires review by the Cardiac Adjudication Committee.

#### 8.2.3.3 Medically Attended Adverse Events

MAAEs are defined as AEs with medically attended visits, including hospital, emergency room, urgent care clinic, or other visits to or from medical personnel for any reason. Routine study visits will not be considered. MAAEs will be reported from the time of study vaccination until Day 29.

#### 8.2.3.4 Pregnancy

Pregnancy is not considered an AE unless there is a suspicion that an investigational vaccine may have interfered with the effectiveness of a contraceptive medication. Any pregnancy that occurs during study participation must be reported using a clinical study pregnancy form. To ensure participant safety, each pregnancy must be reported to Syneos Health within 24 hours of learning of its occurrence. Each pregnancy must be followed up to determine outcome (including

spontaneous miscarriage, elective termination, normal birth, or congenital abnormality) and the status of both mother and child, even if the participant was discontinued from the study. Pregnancy complications and elective terminations for medical reasons must be reported as an AE or SAE. Spontaneous miscarriages must be reported as an SAE.

Any pregnancy brought to the Investigator's attention before the study is completed should be reported to Syneos Health using the pregnancy reporting forms provided to sites.

Any pregnancy brought to the Investigator's attention after the participant has completed the study but occurring while the participant was in the study must be promptly reported to:

[REDACTED]

#### 8.2.3.5 Overdose or Misuse

A drug overdose is defined as the accidental or intentional use of a drug or medicine or an administration error in an amount that is higher than is normally used. Every overdose must be reported to the CRO within 24 hours of awareness, using the details provided in Section 8.3 if the overdose was associated with an SAE. Other overdoses and those associated with non-serious AEs should be reported in the eCRF AE page. Only overdoses associated with a clinical SAE needs to be reported as an SAE. The quantity and duration of the excess dose should be documented in the eCRF.

Overdose in this study is specifically defined as any dose greater than the intended protocol dose (Section 7.1.1.3). In case of overdose, it is recommended that the participant be monitored for any signs or symptoms of adverse reactions or effects and appropriate symptomatic treatment be administered immediately. Note that administration of the "wrong" vaccine is a protocol deviation, but not, in the absence of associated AE, an SAE.

### 8.3 Reporting Adverse Events

All SAEs must be reported according to ICH Good Clinical Practice (GCP) or local regulations, applying the regulation with the stricter requirements. Investigators and other study site personnel must inform the appropriate CRO representatives of any SAE that occurs during the course of the study, from the time of informed consent until the EOS visit, regardless of whether it is judged to be causally related to study vaccine or procedures. Notification must occur within 24 hours of when they become aware of it. AESIs, including PIMMC, myocarditis or pericarditis and AESIs related to COVID-19 are to be reported within these timelines. The investigator should make every effort to obtain follow-up information on the outcome until the event is considered resolved, chronic and/or stable.

SAE reporting forms allow for the notation of other factors that may have impacted the investigator's assessment of causality. Investigators will be instructed to utilize this section of the reporting form to note the impact of an approved/authorized vaccine from a different manufacturer on the event, if applicable. Investigators will be required to report any SAEs in participants who received a different manufacturer's approved/authorized vaccine to local health care and/or regulatory authorities as per the local regulatory guidelines.

If a non-serious AE becomes serious, this and other relevant follow-up information must also be provided to the CRO within 24 hours as described above. The date when the AE becomes serious should be notated in the eCRF or on the SAE form.

All SAEs and AESIs will also be recorded in the eCRF. The investigator is responsible for informing the Institutional Review Board (IRB) of the SAE as per local requirements.

Notification should be made within 24 hours using the dedicated fax line or email for the Syneos Health pharmacovigilance group:

Syneos Health Safety and Pharmacovigilance fax number: [REDACTED]

Syneos Health Safety and Pharmacovigilance email address: [REDACTED]

The report form should be attached to the email or fax; a notification email of the event describing it in the email text is not sufficient. There may be situations when an SAE has occurred, and the investigator has minimal information to include in the initial SAE report. However, it is very important that the investigator always makes an assessment of causality for every event prior to transmission of the SAE report form.

Minimum criteria for a reportable event are:

- Identifiable patient (participant number)
- A suspect product (ie, study vaccine)
- An identifiable reporting source (investigator/study site identification), and
- An event or outcome that can be identified as serious.

Follow-up information on SAEs must also be reported by the investigator within the same time frames.

#### 8.3.1.1 Safety Reporting to Sponsor

Syneos Health will forward the SAE/AESI and pregnancy reports to the Sponsor's safety representative(s) within 1 business day or 3 calendar days (whichever is earlier) of becoming aware of it.

#### 8.3.1.2 Safety Reporting to Health Authorities, Independent Ethics Committees/Institutional Review Boards, and Investigators

Syneos Health will notify the Sponsor of any SAE and will perform follow-up activities with the concerned study site. Syneos Health will retain responsibility of expedited and periodic reporting according to national requirements. Procedure and timelines for safety reporting are provided in the Safety Management Plan as agreed by Syneos Health and the Sponsor. The Investigator must comply with any applicable study site-specific requirements related to the reporting of SAEs (particularly deaths and Suspected Unexpected Serious Adverse Reaction [SUSARs]) to the IRB that approved the study. Investigators should provide written documentation of IRB notification for each report to the CRO. In accordance with ICH GCP, Syneos Health will inform the investigators of findings that could adversely affect the safety of participant, impact the conduct of the study, or alter the IRB's approval/favorable opinion to continue the study, as assessed by the Sponsor. In particular and in line with respective regulations, the CRO will inform the investigators of SUSARs. The investigator should place copies of Safety Reports in the

Investigator Site File. National regulations with respect to Safety Report notifications to investigators will be taken into account. When specifically required by regulations and guidelines, the CRO will provide appropriate Safety Reports directly to the concerned lead IRB and will maintain records of these notifications. When direct reporting is not clearly defined by national or study site-specific regulations, the investigator will be responsible for promptly notifying the concerned IRB of any Safety Reports provided by the CRO and of filing copies of all related correspondence in the Investigator Site File.

#### 8.3.1.3 24/7 Medical Emergency Coverage for Urgent Protocol-related Medical Questions

In a study-related health emergency, when assigned medical monitors for a study cannot be reached by a caller, for discussion of urgent medical questions an on-call physician can be reached 24 hours 7 days a week (24/7):

- Telephone: [REDACTED]

## **9 ANALYSIS**

This section includes a description of the statistical strategy and considerations for the study. Further detailed specifications for the analysis of data from the study will be presented in a Statistical Analysis Plan.

### **9.1 Sample Size Rationale**

The sample size and power are driven by the primary endpoint (ie, lot consistency in terms of immunogenicity measured by IgG response at Day 29). Based on IgG data from Novavax's study 2019nCoV-101 Part 2, previously vaccinated participants in the 18-49-year-old age group who received the SARS-CoV-2 rS vaccine, exhibited an 80% confidence upper bound of Day 29 IgG SD in log10 scale of 0.39. The immunogenic performance of the released lots should be approximately the same, ie, the lot-to-lot GMEU ratio should approximate 1.0. Under any manufacturing practices, between-lot variation exists and is considered normal. Assuming 10% variation (lot-to-lot GMEU ratio is 1.1), an evaluable sample size of 248 subjects for each lot in the per-protocol population will be required to achieve 97% power to demonstrate the lot-to-lot equivalence and provide the overall power of ~90% for all three lot-to-lot equivalence tests (Lot 1 vs. Lot 2, Lot 1 vs. Lot 3, and Lot 2 vs. Lot 3). Accounting for a ~5% dropout rate, a total enrollment sample size of 300 participants will provide 262 participants per lot.

The statistical success criterion for demonstrating the equivalence of each lot (Lot 1, Lot 2, and Lot 3) is based on the IgG response at Day 29. Equivalence will be demonstrated if the 95% CIs of GMEUs for all pairs of lots are within the pre-specified equivalence range of 0.67 to 1.5.

### **9.2 Analysis Sets**

The following analysis sets are identified for analysis.

#### **9.2.1 Randomized Participants Analysis Set**

The Randomized Participants Analysis Set will include all participants who are randomized/enrolled, regardless of whether they actually received any study vaccine. The Randomized Participants Analysis Set will be used for participant disposition summaries and will be analyzed according to the treatment as randomized/enrolled.

#### **9.2.2 Full Analysis Set**

The full analysis set (FAS) will include all participants who are randomized/enrolled and received a dose of study vaccine, regardless of protocol violations or missing data. Participants in the FAS will be analyzed according to the vaccine group as randomized. Immunogenicity summaries and associated statistical analyses will be based primarily on the PP Analysis Set and may also be analyzed in the FAS.

#### **9.2.3 Safety Analysis Set**

The Safety Analysis Set will include all participants who provide consent, are randomized/enrolled, and receive 1 dose of study vaccine. Participants in the Safety Analysis Set will be analyzed as actually treated. The Safety Analysis set will be used for all safety analyses.

#### **9.2.4 Per-Protocol Analysis Set**

The PP Analysis Set will include all participants who receive the study vaccine according to the protocol, have serology results for Day 1 and Day 29 available after the vaccination, and have no major protocol violations that are considered clinically relevant to impact immunogenicity response as determined by Novavax prior to database lock.

The analysis of the primary endpoint will be performed using the PP Analysis Set.

Within the PP Analysis Set there are 3 subsets defined: Anti-S Protein IgG Serology Subset, Neutralization Assay Subset, and the hACE2 Receptor-binding Inhibition Assay Subset.

##### **9.2.4.1 Anti-S Protein IgG Serology Subset**

All participants in the PP Analysis Set who are tested for anti-S protein IgG serology using ELISA prior to study vaccination will be included in this subset.

##### **9.2.4.2 Neutralization Assay Subset**

All participants in the PP Analysis Set who are tested for neutralization prior to study vaccination will be included in this subset.

##### **9.2.4.3 hACE2 Receptor-Binding Inhibition Assay Subset**

All participants in the PP Analysis Set who are tested for ACE2 receptor-binding inhibition prior to study vaccination will be included in this subset.

### **9.3 Statistical Analyses**

#### **9.3.1 Background Analyses**

##### **9.3.1.1 Disposition and Protocol Compliance**

The number of participants consented, randomized/enrolled, and vaccinated will be presented by the study vaccine group for the Randomized Participants Analysis Set.

The number (percentage) of participants in the Randomized Participants Analysis Set, FAS, Safety Analysis Set, and PP Analysis Set who have completed the study (from Day 1 through Day 29) will be summarized overall and by the study vaccine group.

The number (percentage) of participants in the Safety Analysis Set who discontinue the study prior to EOS and the reason for discontinuation (eg, AE, investigator decision, lost to follow-up, non-compliance) will be presented overall and by the study vaccine group. A listing of all participants discontinued from the study will be presented, including the reason for discontinuation and day of last study contact. Day of last study contact will be calculated as follows: date of study discontinuation minus date of Day 1 vaccination +1. A listing of all screened participants who failed the inclusion/exclusion criteria will also be provided.

The number (percentage) of participants in the Safety Analysis Set with major protocol deviations recorded throughout the study will be summarized by study vaccine group and protocol deviation category (Section [11.1.3](#)). A listing of all participants with one or more major protocol deviations will also be provided and will include study vaccine group, study day

associated with the deviation relative to Day 1, protocol deviation category, and a description of the deviation as recorded by the site.

#### 9.3.1.2 Demographics and Baseline Characteristics

Baseline demographic and background characteristics (eg, age, sex, ethnicity, race, height, weight, body mass index [BMI, derived], and ECG) will be summarized overall and by the study vaccine group for the FAS, Safety Analysis Set, and PP Analysis Set. Frequencies and percentages will be presented for categorical variables. Continuous variables will be summarized using descriptive statistics (total number of participants, mean and standard deviation, median, minimum, and maximum).

Medical history will be coded using Medical Dictionary for Regulatory Activities (MedDRA) terms. Baseline medical history recorded at Screening will be summarized by the study vaccine group and by MedDRA System Organ Class/Preferred Term (SOC/PT) for all participants in the Safety Analysis Set. Within each SOC and PT, the number and percentage of participants with at least one medical history event will be presented, respectively. Multiple events within a given SOC and PT for a participant will be counted once.

Participants will also be summarized by the study vaccine group and the name of previous COVID-19 vaccination. In addition, the time between first dose of previous COVID-19 vaccination and Day 1 vaccination dose may be summarized by the study vaccine group using descriptive statistics.

#### 9.3.2 Immunogenicity Analyses

The immunogenicity analysis will be performed using the PP Analysis Set.

For the primary endpoint of IgG (GMEU/mL) to the SARS-CoV-2 spike protein in previously vaccinated participants 18 to 49 years of age, IgG GMEU, geometric mean fold rise ( $\text{GMFR}_{\text{Post/Pre}}$ ), and SCR will be summarized overall and by study vaccine group.

IgG GMEU is calculated as the antilog of the mean of the log-transformed IgG GMEU at Days 1 and 29.  $\text{GMFR}_{\text{Post/Pre}}$  is calculated as the ratio of post-vaccination IgG GMEU at Day 29 to pre-vaccination IgG GMEU at the baseline (Day 1).

Between-group ratio of IgG GMEUs (GMEUR) at Day 29 and the two-sided 95% CIs will be computed using analysis of covariance (ANCOVA), with the study vaccine group as the fixed effect and the ELISA unit at Day 1 (adjusted for intergroup variation in baseline [pre-vaccination] ELISA unit) as the covariate under two-sided type I error rate of 0.05. No type I error rate adjustments will be made. The mean difference of all lots paired comparisons with their corresponding CI limits will then be exponentiated to obtain IgG GMEUR and the corresponding 95% CIs.

As the 1st secondary endpoint of IgG GMEUs (EU/mL) to the SARS-CoV-2 spike protein, SCR (proportion of participants who achieve seroconversion  $\geq 4$ -fold increase from baseline) in IgG GMEUs at Day 29 with corresponding two-sided exact binomial 95% CIs will be calculated using the Clopper-Pearson method. Two-sided 95% CIs of the difference in SCRs in IgG GMEU concentrations for all lots paired comparisons will be based on the Miettinen and Nurminen method.

For the 2nd secondary endpoints of neutralizing antibody response to 3 different lots of NVX-CoV2373 in previously vaccinated participants 18 to 49 years of age, MN50 GMT, GMFRPost/Pre, and SCR will be summarized overall and by the study vaccine group.

MN50 GMT is calculated as the antilog of the mean of the log-transformed MN50 titers at Days 1 and 29. GMFR is calculated as the ratio of post-vaccination MN50 GMTs at Day 29 to pre-vaccination MN50 GMTs at the baseline (Day 1).

Between-group ratio of MN50 GMTs (GMTR) at Day 29 and the two-sided 95% CIs will be computed using ANCOVA, with the study vaccine group as the fixed effect and the titer at Day 1 (adjusted for intergroup variation in baseline [pre-vaccination] titers) as the covariate under two-sided type I error rate of 0.05. No type I error rate adjustments will be made. The mean difference of all lots paired comparisons and comparisons of combined 3 lots with each lot with their corresponding CI limits will then be exponentiated to obtain MN50 GMTRs and the corresponding 95% CIs.

SCR (proportion of participants who achieve seroconversion  $\geq$  4-fold increase from baseline) in MN50 titers at Day 29 with corresponding 2-sided exact binomial 95% CIs will be calculated using the Clopper-Pearson method. Two-sided 95% CIs of the difference in SCRs in MN50 titers for all lots paired comparisons and comparisons of combined 3 lots with each lot will be based on the Miettinen and Nurminen method.

For the 3rd secondary endpoints of antibody responses in a hACE2 receptor-binding inhibition assay, hACE2 GMTs, GMFRPost/Pre, and SCR will be summarized overall and by the study vaccine group (Lot 1, Lot 2, and Lot 3), and between-group hACE2 GMTR and difference in SCRs in hACE2 titers will be calculated using the same statistical methods applied for MN50 titers.

The same statistical methods applied for the analysis of MN50, IgG, and hACE2 may also be applied to characterize the immune response for future vaccine development needs as the exploratory endpoints.

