    tables seroconvind / binomial(exact) alpha=.05;
    output out=out1 binomial;

run;
```

- Two-sided 95% CIs of the difference of SCRs in IgG GMEUs for all pairwise comparisons will be based on the Miettinen and Nurminen method with the following sample SAS code:

```
proc freq data=IgG;
    tables Group*scr / missing riskdiff (cl=MN);

run;
```

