7.1.2 MN₅₀ Titers for SARS-CoV-2

As the 2nd secondary objectives, neutralizing antibody response to the SARS-CoV-2 spike protein in previously vaccinated participants 18 to 49 years of age, the derived/calculated endpoints of MN₅₀ response will include:

- MN₅₀ GMT is calculated as the antilog of the mean of the log-transformed MN₅₀ titers at Days 1 and 29. MN₅₀ GMT will be summarized by the study vaccine group and visit day along with the corresponding 2-sided 95% CIs, by exponentiating the corresponding log-transformed means and their 95% CIs.
- GMFR_{Post/Pre} is calculated as the ratio of post-vaccination MN₅₀ GMT at Day 29 to pre-vaccination MN₅₀ GMT at the baseline (Day 1). Similar sample SAS code as IgG will be applied to estimate MN₅₀ GMFR_{Post/Pre} and corresponding 95% CIs.
- MN₅₀ GMTR between any two of study vaccine groups at Day 29 and the two-sided 95% CIs will be computed using analysis of covariance (ANCOVA), with the study vaccine group as the fixed effect and MN₅₀ titer at Day 1 (adjusted for intergroup variation in baseline [pre-vaccination] MN₅₀ titer) as the covariate under two-sided type I error rate of 0.05. No type I error rate adjustments will be made. The mean difference of all lots paired comparisons with their corresponding CI limits will then be exponentiated to obtain MN₅₀ GMTR and the corresponding 95% CIs. Similar sample SAS code as IgG will be applied to estimate MN₅₀ GMTR and corresponding 95% CIs.
- SCR is defined as proportion of participants who achieve seroconversion ≥ 4 -fold increase from baseline in MN₅₀ titers at Day 29. SCR in MN₅₀ titers with corresponding two-sided exact binomial 95% CIs will be calculated using the Clopper-Pearson method with similar sample SAS code as IgG.
- Two-sided 95% CIs of the difference of SCRs in MN₅₀ titers for all pairwise comparisons will be based on the Miettinen and Nurminen method with the similar sample SAS code as IgG.

7.1.3 hACE2 Receptor-binding Inhibition Titers for SARS-CoV-2

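### The protocol's lot-versus-combined seroconversion intervals treat overlapping samples as independent; the SAP omits that comparison unrecorded, and its sample code does not isolate lot pairs

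*Protocol*

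**What the plan says.** Protocol 9.3.2 treats the assays differently. For IgG, the intervals for differences in "SCRs in IgG GMEU concentrations for all lots paired comparisons will be based on the Miettinen and Nurminen method", so only pairs of lots are compared. For MN50, a second family is added: the intervals "for all lots paired comparisons and comparisons of combined 3 lots with each lot will be based on the Miettinen and Nurminen method". The MN50 GMT ratios get the same addition, but from an analysis of covariance: "The mean difference of all lots paired comparisons and comparisons of combined 3 lots with each lot with their corresponding CI limits" are exponentiated. For hACE2, the between-group GMT ratio and the "difference in SCRs in hACE2 titers will be calculated using the same statistical methods applied for" MN50.

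The SAP keeps only the pairs. SAP 7.1.2 has the MN50 SCR intervals "for all pairwise comparisons will be based on the Miettinen and Nurminen method with the similar sample SAS code as IgG", and SAP 7.1.3 does the same for hACE2. SAP 1.5 says the plan accords with Protocol Version 5.0. SAP Section 12, reserved for departures from the protocol, shows a heading and no text in the copy supplied.

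The sample code in SAP 7.1.1, reused for the other two assays, has two SCR steps. The per-lot rate comes from "tables seroconvind / binomial(exact) alpha=.05", run by Group. The differences come from a single request, "tables Group*scr / missing riskdiff (cl=MN"), with no statement that selects two lots.

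**The concern.** The Miettinen-Nurminen interval adds the variances of two proportions as if they came from different people. In a comparison of one lot with all three lots combined, every participant in that lot is on both sides. The two estimates are positively correlated, so the variance of their difference is smaller than the method supposes and the interval is too wide.

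What is at stake is the reporting of two secondary SCR comparisons. In a consistency study an interval that spans zero may be read as reassurance, and an interval that is too wide spans zero more often than it should.

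There is also a traceability problem. One document specifies the comparison and the other omits it, so a reader cannot tell whether it will be reported. The sample code, meanwhile, does not carry out the pairwise analysis that both documents do agree on.

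**Working it through.** **The plan's own figure.** The documents give no expected SCR, SCR margin or power for these comparisons. The nearest design figure is 97% power per lot pair for the primary IgG test with 248 evaluable per lot (Protocol 9.1, SAP 1.2).
- SE = 0.39 × √(2/248) = 0.0350 on the log10 scale.
- Upper side: (log10 1.5 − log10 1.1)/0.0350 − 1.96 = 0.1347/0.0350 − 1.96 = 1.89, probability 0.970. The lower side is practically certain.
- Power is 97.0% per pair, and 0.9703³ = 91.4% for three pairs. Both agree with the plan.

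**Inputs for the SCR check.** Allocation is 1:1:1 (SAP 1.3), so n per lot is taken as equal. Two values are used: 248, and 300 × 0.95 = 285. Confidence is 95% two-sided. The SCR is an assumption, taken over 0.2, 0.5, 0.8 and 0.9, with no true difference between lots.

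**Variance of lot 1 against the three-lot pool.**
- p1 − (p1 + p2 + p3)/3 = (2/3)p1 − (1/3)p2 − (1/3)p3.
- True variance = (4/9 + 1/9 + 1/9) p(1−p)/n = (2/3) p(1−p)/n.
- Independent-samples variance = p(1−p)(1/n + 1/(3n)) = (4/3) p(1−p)/n.
- The variance ratio is 2, so the width ratio is √2 = 1.41.
- Coverage of a nominal 95% interval = 2Φ(1.96 × 1.414) − 1 = 99.4%.

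**Simulation of the score interval itself** (200,000 runs for each combination of n and SCR).
- Lot against a pool containing it: coverage 99.4% to 99.5%.
- Lot against the other two lots pooled: coverage 94.9% to 95.2%.

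**Size on the percentage scale, n = 248 and SCR 0.8.** The Miettinen-Nurminen half-width for lot against pool is 5.8 points. With the overlap handled it is 1.96 × √((2/3) × 0.16/248) = 4.1 points. At n = 285 the figures are 5.4 and 3.8.

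**Relation between the two differences.** If one lot had an SCR of 70% and the others 80%, the lot-minus-pool difference is 70 − (70 + 80 + 80)/3 = −6.7 points. The lot-minus-other-two difference is −10 points. The first is two thirds of the second by definition.

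**Code, by reading only; it was not run.** Group has three levels, because SAP 7.1.1 lists the three pairs. A Group-by-scr table is therefore 3 × 2 and has no single risk difference; three pairs need three 2 × 2 tables. The rate step does give an exact interval per lot, but names no event level, and the coding of the variable is not stated. If it were coded 0/1 and the procedure reported the first level, an SCR of 80% would appear as 20%. Under another coding it would appear as 80%.

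**The case against.** The strongest reply is that the overlapping interval may never be computed. Protocol Section 9 leaves detailed specifications to the SAP, and the SAP lists pairs only. That stands as a limit on the consequence. It does not settle which document governs, because the SAP claims accordance with the protocol and the supplied text shows no recorded departure.

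Several stronger readings are tempting, and the documents do not support them:
- *That the lot-versus-combined GMT ratios are equally faulty.* They come from an ANCOVA with vaccine group as a fixed effect. A contrast of one lot mean with the average of three, taken within that model, accounts for the overlap.
- *That shrinkage toward zero is a bias.* Lot minus overall mean is a legitimate quantity, different from lot minus the other two. The factor of two thirds is its definition.
- *That the code cannot yield the seroconversion rates.* It yields an exact interval for each lot. Only the event level is left open, and the complement recovers both the rate and its interval.
- *That the MISSING option distorts the tables.* The per-protocol set requires Day 1 and Day 29 serology, so it should matter little there. It could matter in the optional full-analysis-set run.

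The code is also labelled as a sample, and the governing text is clear about pairs. Failing to select two lots would probably be noticed at programming rather than produce a wrong published result. That is fair, but the same sample serves all three assays, so correcting it once is worthwhile.

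**Conclusion.** The point holds in a limited form. As the protocol is written, Miettinen-Nurminen intervals for MN50 and hACE2 SCR differences between a lot and the combined three lots are about 1.41 times too wide, with coverage near 99.4% instead of 95%. The width factor rests on equal lot sizes and a common SCR. The simulated coverage was stable over the assumed SCRs of 0.2 to 0.9.

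The importance is low. The error is conservative in coverage, and the MN50 and hACE2 objectives are to characterise responses, with no margin or success criterion. A reader might infer that the lot-consistency conclusion is threatened. It is not: the primary IgG test and the IgG SCR differences use pairs of lots only.

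Two further items need correcting: the unreconciled difference between protocol and SAP, and sample code that neither isolates a pair of lots nor names the seroconverted level. The remark on SAP Section 12 applies only to the text supplied.

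**What to change.** 1. Drop the lot-versus-combined SCR comparison for MN50 and hACE2, or define it as each lot against the other two lots pooled. The latter samples do not overlap, and the Miettinen-Nurminen interval then has its nominal coverage.
2. Record the choice in SAP Section 12 and bring Protocol 9.3.2 into line. If a lot-versus-combined GMT ratio is kept, state that it is a contrast within the three-group ANCOVA.
3. In the SAP 7.1.1 sample code, run RISKDIFF(CL=MN) on one pair of lots at a time. State how the seroconversion variable is coded, and name the seroconverted level explicitly in both BINOMIAL and RISKDIFF.

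The SAP entry and code changes cost a sentence and a few lines. A change to Protocol 9.3.2 goes through the amendment process in Protocol 10.1 and 10.2, so it is best carried with the next amendment; the SAP entry can record the departure meanwhile. No sample size, visit or data collection changes.
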